According to the CO@h standard operating procedures (SOP),² individuals eligible for onboarding (ie enrolment in the programme) are those diagnosed with COVID-19, either clinically or via a positive test result, who are symptomatic and (i) either 65 years of age or over, or (ii) clinically extremely vulnerable (CEV) to COVID-19. The model of CO@h delivery is primarily implemented in primary care; referrals may additionally be received from the NHS111 COVID Clinical Assessment Service, NHS Test and Trace, and Accident & Emergency (A&E) hospital departments. Patients are encouraged to record three oximeter readings a day; patients should receive text or email prompts or check-in calls to confirm that they are using

the oximeter correctly and that the readings are 95% peripheral oxygen saturation (SpO2) or above. If patients do not show signs of health deterioration within 14 days of onset of symptoms, they are discharged from the programme.

It is estimated that 4% of the population in England are CEV,³ and that approximately 2.4% of the population are CEV and 65 years of age or under. Patients are normally added to the CEV COVID-19 list through an automated process, based on information from patient records. However, GPs are required to periodically review the list to identify registered patients to be added to or removed from it and hospital specialists may also identify additional patients at high risk of health complications from COVID-19. Therefore, clinical judgement may also influence the process, bringing into consideration multiple additional COVID-19 risk factors.

CO@h is also available to care home residents. Training and support for using pulse oximetry is available and there is a CO@h diary (for recording oxygen saturation levels) that has been tailored for care home usage.

At the beginning of February 2021, the CO@h Programme Board recommended to the National Incidence and Response Board (NIRB) to extend the age criteria for CO@h to people aged 50 and over and place more emphasis on clinical judgement. Anecdotally, some areas were already doing this.

Other related interventions

Vaccinations

The roll-out of COVID-19 vaccinations in England started on 8 December 2020. The order of priority for vaccination is, as of 11 February 2021 (with the four highest priority groups being offered a first vaccination by mid-February 2021):^{4,5}

1. Residents in a care home for older adults and their carers

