- Patients in CCGs that are considered to be implementing pulse oximetry in a substantially different way to that set out in the CO@h SOP.² These CCGs will be identified through a combination of sources from the CO@h programme team and checks using the onboarding data. The exact exclusions will be agreed with the CO@h programme team, but are likely to include:
 - CCGs that do not use the 65+ years of age criterion, as set out in the SOP, eg if they only enrol CEV patients. This is because an RDD approach would not be applicable here. If the CO@h programme team or the qualitative evaluation suggests that this may be the case, we can identify such CCGs by checking for a discontinuity in onboarding at age 65 for each CCG independently (data permitting).
 - CCGs that only or mostly implemented a step-down model of CO@h (ie were only providing pulse oximeters at discharge from hospital), as opposed to the pre-hospitalization intervention specified in the SOP. (Note: the step-down model of CO@h differs from the CVWs programme, which is being implemented nationally from January 2021.⁶)

Study period, index dates and follow-up period

The study period start date will differ between CCGs, depending on the following:

- the date CO@h was 'fully operational'
- when patient-level onboarding data are available.

The date of a CO@h service being fully operational is determined by the sites themselves and collected by the Kent, Surrey & Sussex AHSN. It is the date the service was available to all PCNs in the geographical area covered by CO@h (eg the CCG) and does not necessarily mean that that the intervention was being provided to all eligible patients by that date.

We expect that the earliest study period start dates may be at the beginning of December 2020 for some CCGs, as preliminary information suggests CO@h was fully operational in some CCGs at this point and plans were in place to collect patient onboarding data from 1 December 2020. However, due to intense service pressures in January 2021, roll-out may have been delayed in certain areas and there may also be substantial delays to their submissions of onboarding data.

The study period end date can differ between CCGs and may depend on various factors, including some that could affect the validity of the study:

- Changes to the CO@h eligibility criteria. For example, if there is a change to the age threshold, the study period will end prior to the date of this change.

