The null hypothesis for the Fisher-based simulation will assume complete randomisation of patients to treatment within the window. A confidence interval will be estimated for the treatment effect by inverting the calculation for the Fisher-based p-value and identifying values of treatment effect which are not significantly different to the estimated effect. As a comparison to the Fisher-based approach, we will also estimate the p-value using the large-sample Neyman approach based on normal approximation, and also report the power of the Neyman test to inform interpretation.¹⁷ If the results of the Fisher and Neyman approaches differ, we will consider the number of observations within the window to determine which approach is most valid, with the Fisher framework being preferred where sample sizes within the window are small.

Many of our outcomes are binary. In these cases, the estimated treatment effects will comprise differences in mean outcomes on the per cent scale. For our other outcomes, the treatment effects will be differences in mean bed days. As well as the treatment effects, we will also present the point estimates for the treated and control groups in each case. We will not control for the baseline variables in the model, as the window selection procedure will already have been used to identify groups which are comparable in terms of these variables.

Calculation of intervention estimates where outcomes happen before enrolment

This evaluation aims to estimate the effect of pre-hospitalisation CO@h, as detailed in the SOP.² Although we will exclude any CCGs which are identified as only offering enrolment in CO@h at hospital discharge, it is conceivable that other CCGs may offer a combination of pre-hospital and post-discharge as part of the CO@h model, especially in those areas that had implemented a post-discharge model early on in the pandemic. There may therefore be some patients enrolled in CO@h at hospital discharge that we can identify by triangulating date of onboarding with date of hospital discharge. These patients will be considered as not having received the CO@h intervention (ie treatment receipt = 0), similar to those patients enrolled in CVWs (for whom we do not have data).

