COVID-19 vaccinations commenced in December 2020, starting with older care home residents and care home staff, then moving down the priority list. By 15 February 2021, all patients aged 70 and over or CEV should have been offered a vaccination. If vaccinations are effective in stopping people getting COVID-19, this will affect the size of our cohorts, rather than confound our results. However, if vaccinated patients can still get COVID-19 but with milder symptoms (and therefore less likely to require hospital care), this could confound our analysis. We will be provided with information on the roll-out of the vaccinations and will aim to end the study period before or at the point vaccinations start being routinely provided to patients aged 65–70. This will ensure that there is limited confounding close to the threshold. The study period can be, if appropriate, tailored to different areas depending on local vaccination rates.

Some of the outcomes of this study may be difficult to interpret, either because of opposing mechanisms at play or because of other interventions, such as CVWs. However, our primary outcomes, relating to critical care and mortality, are expected to be easier to interpret. The qualitative analysis may also be able to provide contextual information to help interpret our results.

The aim of CVWs is to discharge patients earlier to alleviate the current pressures in hospitals. This could therefore impact on one of the outcomes of the CO@h evaluation: hospital bed days. As we will not have access to data on virtual ward enrolment, we are not able to assess whether CVWs affect patients' total hospital bed days in the CO@h intervention or control groups differently, and therefore whether any difference – or lack of difference – in outcomes is due to CO@h or CVWs. Although patients who are discharged early with CVWs may in general have different characteristics, eg in age, from those that are not, we do not expect a

discontinuity at age 65. Likewise, while CVWs may be used more in areas where there is the most pressure on hospital beds, by virtue of 'treated' and 'control' patients being found within the same areas and hospitals, we do not expect this to cause any bias in our analyses.

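### Coding discharge-onboarded patients as untreated can bias the fuzzy estimate for post-discharge outcomes if step-down onboarding also jumps at 65, and no planned check looks for that jump

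*SAP*

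**What the plan says.** The SAP section *Calculation of intervention estimates where outcomes happen before enrolment* states the target: "This evaluation aims to estimate the effect of pre-hospitalisation CO@h, as detailed in the SOP". CCGs found to enrol solely at discharge are removed, but the section adds that "it is conceivable that other CCGs may offer a combination of pre-hospital and post-discharge as part of the CO@h model", and those CCGs stay in. Patients whose dates show enrolment at discharge remain in the cohort under this rule: "These patients will be considered as not having received the CO@h intervention (ie treatment receipt = 0), similar to those patients enrolled in CVWs". No exception by outcome is given. The same section handles A&E referrals differently. For them, receipt is 0 for the A&E attendance that came before onboarding and 1 for a later emergency admission.

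Other sections bear on the rule:

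- *National roll-out of CO@h* gives the entry criteria for the programme as a whole: "individuals eligible for onboarding (ie enrolment in the programme) are those diagnosed with COVID-19", with symptoms, who are "either 65 years of age or over, or (ii) clinically extremely vulnerable (CEV) to COVID-19". CEV patients are excluded from this analysis, so age 65 is the operative criterion.
- *Study cohort* (area-level exclusions) expects to drop CCGs that do not apply the age criterion and CCGs whose service was wholly or largely step-down. It also notes that "the step-down model of CO@h differs from the CVWs programme".
- *Sharp and fuzzy designs* bases the fuzzy analysis on a comparison by assignment, that is, by side of the threshold.
- *Strengths and limitations* discounts bias from CVWs because no discontinuity in their use is expected at 65. It says nothing equivalent about step-down CO@h.

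**The concern.** A fuzzy design attributes the whole outcome difference at the threshold to the treatment as coded. The SAP relies on this when it assumes, under *Strengths and limitations*, that nothing else in care changes at 65. Once discharge onboarding is coded 0, it becomes such another difference if it too is triggered by age 65. The patients leave the enrolment jump, but their outcomes stay in the age contrast.

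The SAP accepts this logic for the PRINCIPLE trial. Because that trial shares the threshold, the SAP says findings may mix the two effects, plans to examine the overlap, and aims to end the study period before 5% of patients in the window have enrolled. Step-down CO@h gets no comparable check, although patient-level dates for it are expected.

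The main analysis is at stake for outcomes that can occur after discharge: death (primary), critical care use and days after discharge (primary), and emergency bed days from readmission. Readmission is not an outcome in its own right. For a patient whose index stay was an emergency admission within follow-up, the admission indicator is already 1.

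**Working it through.** **The plan's own figures.** The SAP gives no figure on this point. Its one reproducible calculation is Table 1, which is not in dispute. With pooled variance, two-sided 5% and 80% power, 2% against 1.5% needs [1.960 × √(2 × 0.0175 × 0.9825) + 0.8416 × √(0.0196 + 0.014775)]² / 0.005² = 10,795 per group, or 21,590 in total, as printed. All 21 cells reproduce.

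**Formula.** Let d_p and d_s be the jumps at 65 in pre-hospital and discharge onboarding, and t_p and t_s their effects on an outcome after discharge.

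- Outcome contrast at 65: d_p × t_p + d_s × t_s
- Enrolment jump with discharge onboarding coded 0: d_p
- Fuzzy estimate: t_p + (d_s/d_p) × t_s

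The bias is (d_s/d_p) × t_s. It is zero if d_s = 0 or t_s = 0.

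**Illustration for death.** The true pre-hospital effect is set at −0.25 points: the pilot's 1% mortality (*Power calculation*) with the 75% relative risk of Table 1. The SAP gives none of the other inputs. The assumed ranges are d_p 5% to 40%, d_s 0 to 2.5% and t_s 0 to −1 point.

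| d_p | d_s | t_s (points) | Bias (points) | Estimate (points) | Ratio to truth |
|---|---|---|---|---|---|
| any | 0 | any | 0 | −0.250 | 1.00 |
| 40% | 0.5% | −0.5 | −0.006 | −0.256 | 1.02 |
| 20% | 1% | −0.5 | −0.025 | −0.275 | 1.10 |
| 10% | 2.5% | −1 | −0.250 | −0.500 | 2.00 |
| 5% | 2.5% | −1 | −0.500 | −0.750 | 3.00 |

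The bias column is also what would be credited to pre-hospital CO@h if its true effect were zero.

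**Worked case with t_p = 0.** Take 5% admitted (the pilot figure) and d_p = 10%. Assume that half of admitted patients aged 65 or over who are not already enrolled are onboarded at discharge, with none below 65, and that death falls from 4% to 3% with step-down.

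- d_s = 0.05 × 0.90 × 0.50 = 2.25%
- Outcome contrast = 0.0225 × (−1) = −0.0225 points
- Receipt coded as planned: −0.0225/0.10 = −0.225 points
- Any onboarding coded 1: −0.0225/(0.10 + 0.0225) = −0.184 points

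A simulation of the same case gave −0.22 and −0.18. The last line shows that the wider coding yields a combined effect. It does not recover the pre-hospital effect, which is zero here.

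**Would a planned check reveal d_s?**

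- Diagnostic check 1 plots all onboarding by week of age, without splitting by route.
- The check under *Sources of data* that onboarding is mainly pre-hospital measures a share, not a jump at 65.
- The step-down exclusion under *Study cohort* leaves mixed CCGs in.
- The flow diagram counts patients by route, not by age.
- The placebo study period precedes CO@h, so step-down begun as part of CO@h is absent from it. It also runs only if the sharp analysis is significant.

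**The case against.** The strongest objection is that the premise is not in the SAP. Nowhere does it say that discharge onboarding followed the age-65 rule. It calls mixed models only conceivable, chiefly in areas with an early post-discharge service, and those may have used other criteria. This stands. A reader might infer that a step-down effect is bound to be credited to pre-hospital oximetry, but the document supports only the conditional statement.

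Second, the comparison with CVWs may only explain the coding, since neither group received the pre-hospital service. That is a fair reading. The gap remains, because the only stated reason for treating post-discharge support as harmless is the no-discontinuity argument, and that covers CVWs alone.

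Third, a reader might infer that step-down shortens the index stay and so acts directly on bed days. The SAP does not say so. Earlier discharge is its description of CVWs, and its remark "This could therefore impact on one of the outcomes of the CO@h evaluation: hospital bed days" concerns them. Step-down CO@h is described only as supplying oximeters at discharge.

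Fourth, receipt = 0 is correct for anything before discharge, including critical care in the index stay. This stands.

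Fifth, a reader might fault the sharp analysis for mixing the two routes. It estimates the effect of eligibility, so including every route that eligibility opens is proper.

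Finally, the CCG exclusions and the check that onboarding is mainly pre-hospital will reduce the problem. They do not test for the jump that decides whether there is bias.

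**Conclusion.** The point holds conditionally. If discharge onboarding in the retained mixed-model CCGs jumps at 65, and step-down affects outcomes after discharge, the planned coding makes the fuzzy estimate t_p + (d_s/d_p) × t_s instead of t_p. The general onboarding rule and the planned exclusion of CCGs that do not use the age criterion make such a jump plausible, but the SAP does not establish it.

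The size cannot be derived from the document. Over the assumed ranges the mortality estimate runs from 1.0 to 3.0 times a true −0.25 points. The upper end needs a pre-hospital jump of only 5% with a step-down jump half as large. Only mixed CCGs contribute step-down patients, so the pooled bias may be small. The defect is that the deciding condition can be tested with data the SAP already plans to use, and the plan does not test it.

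**What to change.** 1. Add to diagnostic check 1 a plot of discharge onboarding by week of age over the whole cohort, with an estimate of its jump at 65 pooled over the retained CCGs. CCG-level jumps would rest on few patients and should not be used to select areas.
2. Add a sensitivity analysis for death and the other post-discharge outcomes that codes any CO@h onboarding preceding the outcome as receipt = 1. This follows the outcome-timing logic already used for A&E referrals. Label it as the combined pre-hospital and step-down effect. Keep receipt = 0 for events before discharge.
3. If a jump is found, either repeat the main analysis in CCGs below a step-down share of onboardings that is fixed before outcomes are seen, or label the main estimate as combined.
4. State that the no-discontinuity argument applies to CVWs and is not relied on for step-down CO@h.

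The cost is some SAP wording, one plot and one or two extra runs. The onboarding and discharge dates are already to be triangulated. The restricted run loses precision in a study that the SAP already fears is underpowered.

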4. **Check that CEV and care home patients should be excluded.** We will also check for an age-related discontinuity in onboarding of CEV and care home residents and exclude these patients from the analysis if there is no discontinuity to exploit at age 65:
 - CEV (yes/no)
 - Care home residents (yes/no)

Window selection

Although we expect there to be a trend in the proportion of patients with certain characteristics by age (eg multimorbidity, diabetes), the local randomisation approach assumes there is a window around the threshold where there are no statistically significant differences between treated and control patients. The symmetric window around the threshold that we will use in our analysis will be identified through a data-driven approach formulated by Cattaneo et al.¹⁷ The baseline variables will be exploited to identify the largest window around the age 65 threshold within which there is no evidence that the patients vary significantly between groups in terms of those baseline variables. By identifying this window, an age range is identified across which the groups of patients can be said to be comparable at baseline. These patients are then used in the main analysis to estimate treatment effects. This method assumes that the baseline variables adequately account for differences in pre-intervention characteristics within this window that might affect outcomes and vary by age. This assumption implies that the outcomes are conditionally independent of the baseline variables.

The window will be identified by first conducting tests of mean differences in the baseline variables at the narrowest window – ie 1 week either side of the age 65 threshold, and with a minimum of 10 observations (patients) per group. Each baseline variable will be tested and the smallest resulting p-value reported. The window will then be increased by 1 week either side of the threshold and the process repeated. The maximum window used in the main analysis will be the smaller of (a) the one immediately prior to the window where a statistically significant

difference between groups is first identified, or (b) the one where the sample size achieved should comfortably identify a statistically significant difference in the outcome based on power calculations*.

Although we believe that the window will be determined by (a), the criterion in (b) will ensure that any potential for unobserved confounding caused by the use of a very wide window is limited.

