For the procedure in (a), Cattaneo et al recommend that the p-value chosen for these tests is at least 0.10 and preferably 0.15.¹⁷ As we have a large number of baseline characteristics, a p-value of 0.10 should provide a reasonably conservative threshold, given that the chances of identifying a significant difference in at least one variable increase with the number of variables tested.²³ The results of these tests will be tabulated and plotted, showing how the minimum p-value changed against each window length from a window length of 1 week either side, up until the resulting minimum p-value remains consistently below 0.05.

Although the window selection can be done directly through the 'rdrandinf' command (within the 'rdlocrand' R package), we will calculate it using the separate window selection function 'rdwinselect', so that the window selection process is completed independently of the main analysis.²⁴

Baseline variables

The baseline variables that we will check and use to identify the age window for analysis are:

- Gender
- Ethnicity
- IMD quintile
- IMD health deprivation and disability quintile
- Smoker (yes/no)
- Obesity (yes/no)
- Diabetes (yes/no)
- Multimorbidity (yes/no), ie whether a patient had two or more long-term conditions. We will use the list of conditions in the Cambridge Multimorbidity Score,²⁵ based on a list of conditions recorded in GP records and available in GDPPR and also used in Stafford et al²⁶.
- Region – as a proxy for other unobservable characteristics, as regions may have differing rates of COVID-19 and therefore also hospital pressures, which may affect patients' outcomes.

* Using power = 80%, alpha = 5%, and two-sided test.

Main analysis

In the main analysis, we will estimate a treatment effect based on the difference in means between the treated and untreated. Using randomisation inference, 10,000 simulated draws based on Fisher's exact approach to null-hypothesis testing will be used to estimate p-values of zero effect. We do not expect to have to transform the outcomes – as we do not expect the outcomes to vary with age within the chosen window – therefore we will use a polynomial of order zero (ie a constant within-group average outcome, which is the standard in the local randomisation approach. The plots created in the prior descriptive analysis will be used to confirm this).

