Patients who have a COVID-19 positive test and are subsequently enrolled without any intermediate hospital activity will be considered 'treated' for the purpose of all hospital outcome analyses which occur within 28 days of the date of their first COVID-19 positive test. If a patient attends A&E after enrolment but before they received a pulse oximeter, they will still be considered as having received the intervention. This is because the evaluation seeks to understand the usefulness of CO@h as it is used in practice.

However, A&E departments are also one of the services that can refer patients to CO@h. In this case, the A&E attendance by definition pre-dates onboarding (as the pulse oximeter was dispensed following A&E attendance). Here, it is not appropriate to count the patient as having had the intervention when analysing A&E attendances. However, it is also not appropriate to exclude these patients from the analysis for outcomes that occur before onboarding, as this would introduce bias compared with patients not enrolled in CO@h. We can identify the cases described above by triangulating the date of onboarding with any dates of A&E, thereby determining whether patients were (most likely) enrolled through A&E. Using these data, we can set the intervention receipt (which is used in the fuzzy part of the design) to 1 (enrolled) or 0 (not enrolled) depending on the outcome – ie for a patient enrolled following an A&E attendance, this attendance would still count towards the outcome in the model for A&E attendances, but treatment receipt (enrolled) would be set to 0. However, for the emergency admission outcome, the same patient's subsequent emergency admission (if one occurred) would have enrolment set to 1.

Sensitivity analyses

We will undertake a range of sensitivity analyses to identify whether the resulting treatment effect estimates are reliable. These will be carried out on each of the primary outcomes (critical care bed use, total bed days in critical care, and death) but only on the secondary outcomes if these show statistically significant treatment effects. Unless otherwise stated, the design choices used in the main analysis (eg fuzzy design, window, order of polynomial, etc) will be the same as in the main analysis. The sensitivity analyses will include:

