1. Intention-to-treat analysis – we will use a sharp design (without taking account of compliance/oximeter receipt) to estimate the average effect of intervention eligibility at age 65, ie an intention-to-treat analysis.
2. Placebo outcomes – we will undertake statistical tests for treatment effects for each of the baseline variables and plot the means for each group, weekly averages and fitted constants to identify any evidence of infringement of the assumption of comparability of the groups.
3. Test of treatment assignment – we will use a binomial test to check that, within the specified window, treatment can be considered randomly assigned.
4. Influence of window choice – we will test a selection of windows smaller than the one used in the main analysis (minimum 10 patients either side of the threshold). We will not use larger windows as this may lead to biased estimates due to imbalances in baseline variables.¹⁷ By using smaller windows, this problem is avoided while also identifying whether restriction of the cohort to those increasingly closer to the threshold affects the treatment effect estimates. We will plot the resulting point estimates and confidence intervals.
5. Placebo thresholds – we will estimate treatment effects at both a lower and a higher threshold than age 65 to check that these spurious, placebo thresholds result in a treatment effect of zero. For these checks, we will only use control and treated patients,

respectively.¹⁷ We will test at thresholds centred on the first mass point past the end boundaries of the window used in the main analysis. We will use the same window size (ie number of mass points either side) as in the main analysis.¹⁷

6. Placebo study period – we will use data for a period before CO@h was implemented (ie in CCGs before they implemented CO@h) to check that there is no discontinuity in outcomes in a window around age 65 when no treatment was available. This will be a sharp RDD (as there will, by definition, be no intervention available). This sensitivity analysis will only be conducted if the intention-to-treat analysis using a sharp RDD (sensitivity analysis #1) is statistically significant.
7. Sensitivity to unmeasured confounding – we will calculate Rosenbaum’s sensitivity bounds, within the context of a local randomisation RDD, to estimate how large an unobserved confounder would need to be to affect the conclusions of the study.^{19,27}

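### The placebo-outcome tests reuse the variables that chose the window, and the placebo-threshold check inherits a fuzzy design where no enrolment jump is expected

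*SAP*

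**What the plan says.** **Window.** Under Window selection, the window grows by one week on each side of age 65. At each step, "Each baseline variable will be tested and the smallest resulting p-value reported". The final window is the smaller of two. The first is "a) the one immediately prior to the window where a statistically significant" difference between the groups appears; the second is a cap set by power. On the cut-off, the SAP says that "a p-value of 0.10 should provide a reasonably conservative threshold". The section Baseline variables opens its list with "The baseline variables that we will check and use to identify the age window for analysis are" and names nine: gender, ethnicity, two deprivation quintiles, smoking, obesity, diabetes, multimorbidity and region.

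**Item 2 of Sensitivity analyses (placebo outcomes).** "we will undertake statistical tests for treatment effects for each of the baseline variables". The item adds that the authors will "plot the means for each group, weekly averages and fitted constants". Its stated aim is to detect a breach of group comparability. It names no variable outside the list.

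**Item 5 (placebo thresholds).** "We will test at thresholds centred on the first mass point past the end boundaries of the window used in the main analysis". The window size is kept and the effect should be zero. The item does not say whether it is sharp or fuzzy. The opening paragraph of the section supplies the default: unless an item says otherwise, "the design choices used in the main analysis (eg fuzzy design, window, order of polynomial, etc) will be the same" as in the main analysis. Items 1 and 6 are declared sharp; item 5 is not.

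**Fuzzy design.** Sharp and fuzzy designs allows the fuzzy approach only where receipt changes abruptly at the threshold. It is run through the Anderson-Rubin statistic, compared by assigned group.

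**The concern.** Item 2 asks the same variables the same question in the same window that they were used to choose. A pass is settled in advance. If it is reported as separate support for comparability, one piece of evidence is counted twice. This matters more because the Main analysis section omits covariate adjustment on the strength of that same window selection.

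Item 5 promises to estimate effects and see that they are zero. Each placebo threshold lies wholly on one side of 65, where enrolment should not jump. A complier effect divides the outcome difference by the enrolment difference, so here it divides by something whose expected value is zero.

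There is also a conditional issue. The upper placebo comparison may take in people aged 70 or over, whom the SAP expects to have been offered vaccination by 15 February 2021, the date until which it expects at least to be able to use data.

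**Working it through.** **1. Calibration against the SAP's own figure.** Table 1 gives a total of 21,590 for 2% v 1.5% (two-sided 5%, 80% power). Per group, n = [1.960 x sqrt(2 x 0.0175 x 0.9825) + 0.8416 x sqrt(0.02 x 0.98 + 0.015 x 0.985)]^2 / 0.005^2 = 10,795, and twice that is 21,590. All 21 cells of Table 1 reproduce. At the worked example's 11,000 per group, power is 80.7%.

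**2. Item 2 by logic.** Selection stops before the first window whose smallest p is under 0.10. So all nine variables have p of at least 0.10 in the chosen window and in every narrower one; the power cap can only move to one of those. Item 2 keeps that window and the order-zero comparison. If it is also run as fuzzy, its test of zero effect is still the comparison by side (step 5). Monte Carlo error does not alter this: with 10,000 draws, the standard error of a p-value of 0.10 is sqrt(0.10 x 0.90 / 10,000) = 0.003. The Benjamini-Hochberg adjustment can only raise p-values.

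**3. Item 2 by simulation.** Assumed inputs: nine independent binary variables with assumed prevalences; 30, 100 or 300 patients per week per side; with and without age trends; with and without a true 5-point jump in multimorbidity at 65; 2,000 runs for each of 12 scenarios.
- Between 508 and 799 runs per scenario yielded a window; the rest yielded none.
- Re-tests with p below 0.05 in the chosen windows: 0 in every scenario. The smallest p was 0.1000.
- For contrast, a fixed 52-week window with age trends gave at least one p below 0.05 in 65% to 100% of runs.
- Without prior selection, nine independent null tests would flag at least one variable with probability 1 - 0.95^9 = 37.0% at 5%, or 1 - 0.90^9 = 61.3% at 10%.

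**4. Item 5, estimate and interval.** Complier estimate = (outcome difference by side) / (receipt difference by side). With 11,000 per side, receipt of 5% on both sides (assumed), an outcome risk of 2% on both sides and 20,000 runs:
- 2.5th to 97.5th percentiles of the estimate: about -6.3 to +6.6, on an outcome that runs from 0 to 1;
- undefined (zero denominator) in 1.2% of runs;
- 95% set bounded in only about 5% of runs, since that needs a receipt difference that is itself significant.

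The range was about -12 to +12 at 1% receipt and -3.4 to +3.6 at 30%.

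**5. Item 5, p-value.** For a hypothesised effect t, the Anderson-Rubin test compares (outcome - t x receipt) between sides. At t = 0 receipt drops out, leaving the plain comparison of outcomes by side. At 11,000 per side it rejected in 5.0% to 5.2% of runs with no outcome difference, and in 80% to 81% at 2% v 1.5%, for each receipt rate tried. At 1,000 per side the latter was about 14%.

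**6. Upper placebo comparison.** With a half-width of w years, the upper threshold sits just past 65 + w and the comparison runs to about 65 + 2w. It reaches age 70 when 2w exceeds 5, that is, when w exceeds about 2.5 years. At the anticipated w = 5, it would compare roughly 65-70 with 70-75.

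**The case against.** A reader might infer that neither check can falsify the design. The SAP does not support that. Its fuzzy analysis rests on an Anderson-Rubin test of zero effect, which needs no enrolment jump and keeps its size and power (step 5); item 5's p-value can reject, and its limit is sample size. Declaring the item sharp leaves that p-value unchanged. Item 2's plots of weekly averages can still show a trend or jump, and the baseline variables can already count against the design during window selection.

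The fuzzy reading of item 5 comes from a general default sentence. Item 5 also limits the two checks to control and treated patients respectively. If that means actual receipt rather than side of 65, receipt is constant, the ratio is undefined and only a sharp comparison is possible. This is a further reason to state the design.

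A reader might also infer that the upper placebo threshold must fall on the vaccination cut-off at 70. Five years is only what the authors anticipate; the actual window is data-driven and may be far narrower. The SAP describes 15 February as a government aim and a date by which vaccination should have been offered, not as completion. Nor is there a matching case for age 60: that group follows the 65-and-over group in the priority list, and the study aims to end by the time routine vaccination at 65-70 begins.

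Finally, other checks remain: the binomial test, smaller windows, Rosenbaum bounds and a conditional placebo period. They do not fill item 2's gap. The binomial test looks only at counts, the smaller windows have all passed the same selection test, and the placebo period runs only if the sharp analysis is significant.

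**Conclusion.** The point holds in two limited parts.

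- **Item 2:** the formal tests are fixed by window selection and add no independent evidence. This follows from the rule itself, not from the simulated inputs. It assumes the same test and coding at both stages; a different coding of ethnicity or region could shift individual p-values.
- **Item 5:** the inherited fuzzy estimate and interval are uninformative, while the p-value for zero effect is sound. The sizes in step 4 depend on the assumed receipt rates; the conclusion needs only that enrolment does not jump at the placebo threshold.

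The vaccination issue arises only if the half-width exceeds about 2.5 years. No primary estimate, p-value or window changes. What is at stake is how much weight the report can place on these two checks.

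**What to change.** 1. **Item 2:** run the tests on variables not used to select the window. Calendar week of the index test is available, because the full test date is supplied. A&E attendance or emergency admission before the index date would also serve where the extract has look-back, which Sources of data does not state. Individual conditions are a weaker option, since they feed the multimorbidity flag. Keep the plots, and label re-tests of the nine selection variables as descriptive.
2. **Item 5:** declare it a sharp (eligibility) comparison, as item 6 is, and define the groups by side of the placebo threshold, not by receipt.
3. **Vaccination:** if the selected window makes the upper placebo comparison include people aged 70 or over, limit that comparison to index dates before their vaccination roll-out, or interpret it with that in mind.

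The cost is SAP wording, a small amount of extra analysis, and fewer patients in the upper placebo comparison if dates are restricted.
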